### 9.2.2 Secondary analysis

A similar ANOVA, as described in [Section 9.2.1](#), will be performed on log-transformed  $t^{1/2}$  to compare elimination characteristics between treatment groups (i.e., Test 1 versus Reference 1 and Test 2 versus Reference 2).

The point estimate and the 90% CI for the median treatment differences for  $t_{max}$  will be computed according to the Hodges-Lehmann's method.

### 9.2.3 Sensitivity analysis

The following sensitivity analyses will be performed following the same model as described for the primary analysis (Section 9.2.1):

1. Based on all nonpositive ADAb participants (Defined as any positive ADAb observed post baseline)
2. Including body weight at Day -1 as covariate
3. Corrected for measured protein content:

For compliance with Canadian Health ministry guidance, AUC and  $C_{max}$  ratio estimates and 90% CIs will be also presented as corrected for measured protein content (potency). A correction factor (CF) will be obtained as the ln-transformed ratio of the percent protein content (Reference/Test). Then, this factor will be added to the difference in LSMS to obtain, by exponentiation, the corrected AUC and  $C_{max}$  geometric mean ratios and its 90 % CIs.

For a given Reference/Test, the correction factor will be calculated using the below formula:

$$CF = 100 \times \exp\left(\frac{\% \text{ Measured Content Reference}}{\% \text{ Measured Content Test}}\right) \quad [4]$$

The corrected ratio estimate for the PK parameter (AUC or  $C_{max}$ ) is calculated using the below formula:

$$Ratio = 100 \times \exp(LSM \text{ difference} + CF) \quad [5]$$

Where,

$$LSM \text{ difference} = LSM(\text{Test}) - LSM(\text{Reference}) \quad [6]$$

The corrected 90% CI for the ratio is obtained using the below formula:

$$90\% \text{ CI} = 100 \times \exp[(LSM \text{ difference} + CF) \pm t_{0.05,n} \times se(LSM \text{ difference})] \quad [7]$$

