## 9.2 Statistical analysis of bioequivalence

### 9.2.1 Primary analysis

The primary PK parameters (AUC,  $AUC_{(0-t)}$  and  $C_{max}$ ) will be evaluated according to a univariate model of analysis of variance (ANOVA). The model will include treatment group as a fixed effect. The dependent variables will be logarithmically transformed by natural logarithms ( $\ln$ ) prior to analysis.

Two independent comparisons will be made:

- Test 1: Bimekizumab-SS-2mL versus Reference 1: Bimekizumab-SS-2x1mL
- Test 2: Bimekizumab-AI-2mL versus Reference 2: Bimekizumab-AI-2x1mL

For each comparison, the difference between the least squares means (LSM) will be estimated and back transformed in order to obtain the geometric mean ratio for the corresponding Test/Reference together with the 90% CI for the ratio.

For each of the respective comparisons, BE will be concluded if the 90% CIs for the ratio of the respective comparison are fully included in the acceptance range from 0.8 to 1.25 for AUC,  $AUC_{(0-t)}$  and  $C_{max}$ .

All participants in the PK-PPS will be included in the analysis as far as the data permit; a participant may be included in the analysis for one or more PK variables (i.e., if it was not possible to calculate AUC for a given participant, the participant may be included in the analysis of BE for  $AUC_{(0-t)}$  and  $C_{max}$ ).

The results of the BE analysis will be tabulated, for each comparison, including the geometric least squares means and 90% CI for treatment group, the estimated geometric mean ratio and 90% CI for the corresponding Test/Reference as well as the CV%.

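### SAP formula [4] for the protein-content correction prints CF = 100 × exp(Reference/Test), where the text and formulas [5] and [7] need CF = ln(Reference/Test)

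*SAP*

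**What the plan says.** SAP 9.2.3, item 3, commits to presenting the AUC and Cmax ratios and their 90% CIs corrected for measured protein content, to comply with Canadian guidance. It defines the correction factor twice.

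- **In words:** "A correction factor (CF) will be obtained as the ln-transformed ratio of the percent protein content (Reference/Test"). On its use: "this factor will be added to the difference in LSMS to obtain, by exponentiation, the corrected AUC" and Cmax ratios with their CIs.
- **As a formula:** "For a given Reference/Test, the correction factor will be calculated using the below formula". Formula [4] then reads CF = 100 × exp(% measured content Reference / % measured content Test).

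Formula [5] gives the corrected ratio as 100 × exp(LSM difference + CF). Formula [6] defines the LSM difference as Test minus Reference. Formula [7] puts the same sum inside the exponent and adds the usual ± t × se term. SAP 9.2.1 fixes the scale of the LSMs: "The dependent variables will be logarithmically transformed by natural logarithms".

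**The concern.** The log of a ratio and 100 times its exponential are different quantities, and formula [4] is the one presented as the calculation rule. A programmer who codes the formulas as printed produces an unusable table for an output that the SAP promises. The SAP is the programming specification, and nothing later in it settles the conflict: CF otherwise appears only in the abbreviation list, and the SAP's amendment section holds placeholder text.

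**Working it through.** **Inputs from the SAP**

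- LSM difference on the natural-log scale (9.2.1), so LSM difference = ln(GMR), where GMR is the uncorrected Test/Reference geometric mean ratio.
- CF by the text: ln(R/T), where R and T are the percent measured contents of Reference and Test.
- CF by formula [4]: 100 × exp(R/T).
- Corrected ratio by formula [5]: 100 × exp(LSM difference + CF), in percent.

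**Inputs not in the documents**

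- The measured contents. The R/T pairs below are assumptions.
- The uncorrected ratio, taken here as 0.95, one of the two planning ratios in SAP 2.4.

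The SAP states no numerical CF, so there is no figure to reproduce. The check is which definition makes formula [5] do what the text describes.

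**Step 1: algebra.** With the text's definition, [5] gives 100 × exp(ln GMR + ln(R/T)) = 100 × GMR × R/T. That is the content-corrected ratio in percent. The direction is also right: a Test product with more protein than Reference has R/T below 1, so its ratio is scaled down.

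**Step 2: equal contents (R/T = 1).** No correction is due.

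- Text: CF = ln(1) = 0, and the ratio is 100 × 0.95 = 95.0%.
- Formula [4]: CF = 100 × e = 271.83. Then log10 of the ratio = 2 + (ln 0.95 + 271.83)/ln 10 = 2 + (−0.051 + 271.83)/2.3026 = 120.03, so about 10^120 %.

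**Step 3: unequal contents (assumed), GMR 0.95.**

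| R/T | CF, text | Ratio, text | CF, formula [4] | Ratio, [4] with [5] |
|---|---|---|---|---|
| 95/105 | −0.1001 | 85.95% | 247.13 | about 10^109 % |
| 100/100 | 0 | 95.0% | 271.83 | about 10^120 % |
| 105/95 | 0.1001 | 105.0% | 302.00 | about 10^133 % |

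Each value in the text column equals 95 × R/T, as Step 1 requires. In formula [7] the CF shifts both confidence limits by the same amount as the point estimate, so the limits fail in the same way.

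**Step 4: both parts of [4] have to change.**

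- Drop the 100 but keep exp: at equal contents CF = e = 2.718 and the ratio is 1439.7%.
- Change exp to ln but keep the 100: for 99/101, CF = −2.000 and the ratio is 12.9% (correct 93.1%); for 101/99, CF = 2.000 and the ratio is 702% (correct 96.9%). This version is right at equal contents, so a program test on equal contents alone would pass it.

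**Step 5: does the correct version matter?** Take the planning values in SAP 2.4 (GMR 0.90, CV 33%, 93 per group).

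- SD on the log scale = sqrt(ln(1 + 0.33²)) = 0.3215.
- se = 0.3215 × sqrt(2/93) = 0.0471, with t on 184 df for a two-group comparison.
- Uncorrected result: 90.0% (90% CI 83.3 to 97.3).
- With assumed contents 98/102, CF = −0.040 and the result is 86.5% (79.99 to 93.48).

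A content difference of that size would bring the lower limit to the 80% boundary, so the corrected CI can carry information.

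**The case against.** The strongest reply is that the method is already specified correctly. The sentences just above formula [4] give the right definition and the right use, so only the typeset restatement is wrong. CF enters neither the primary rule, "BE will be concluded if the 90% CIs for the ratio of the respective comparison are fully included in the acceptance range", nor the sample size. A ratio near 10^120 % could not survive review. The assumed contents are illustrative, and nobody has proposed the partial repairs in Step 4. The 100 × exp prefix also matches [5] and [7], so it could be a copying slip or even an artefact of reading the PDF.

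Most of this stands as an argument about weight, and it is why the point is minor. It does not remove the contradiction. Equal contents expose the fault without assuming any content difference. A simple misreading of ln as exp would not explain the leading 100, although a check against the source file is still sensible.

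One further caution is fair. Formula [7] writes the t quantile with subscript n, which the SAP's abbreviation list defines as the number of participants with available measurements rather than the degrees of freedom. That is a separate notational matter with negligible numerical effect at about 93 per group. The statement here is only that CF enters [5] and [7] correctly.

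**Conclusion.** The point holds. Formula [4] contradicts the text of its own section and is the line in error, because the text, the natural-log scale in 9.2.1 and formulas [5] to [7] all fit CF = ln(Reference/Test). At equal contents the printed CF is 271.8 where it should be 0. At an assumed uncorrected ratio of 95%, the printed formulas return about 10^120 %, and about 10^109 to 10^133 % if each content lies between 95% and 105%; the correct range is 86.0% to 105.0%. The percentages depend on the assumed ratio and contents, but the contradiction does not. Severity is minor: one committed sensitivity output would be unusable if coded as printed, while the primary bioequivalence conclusion is untouched.

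**What to change.** Check formula [4] against the source file. If it is printed there as here, replace it with CF = ln(% measured content Reference / % measured content Test), with no factor of 100. The way CF enters [5] and [7] needs no change.

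If the program already exists, confirm that it uses the log definition, and test it with unequal as well as equal contents.

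The cost is one line, with no new data or output. SAP section 1 requires an amendment when analysis definitions are modified or updated before database lock. A correction that restores the stated text may not count as a modification, but at most it needs a short amendment.

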## 10 IMMUNOGECITY ANALYSIS

### 10.1 Anti-drug antibodies

ADAb will be measured using a 3-tiered assay approach: screening assay, confirmatory assay and titration assay.

A screening cut point will be determined by the bioanalytical laboratory that will be used to determine the status of ADAb as above the cut point (ACP) or below the cut point (BCP). Samples presenting ADAb levels ACP are considered "potentially ADAb positive" and will be further evaluated in the confirmatory assay, the result of which will be reported as either "confirmed positive" (CP) or "not confirmed positive" (NCP). Confirmed positive samples (reported as CP) will be titrated, and the titer (reciprocal dilution factor including minimum required dilution) reported.

ADAb status at any time point:

- An ADAb status of positive (ADAb+) will be concluded for any participant with an ADAb level that is ACP and CP;
- An ADAb status of negative (ADAb-) will be concluded for any participant with an ADAb level that is either BCP or ACP and NCP;

Participant Classification:

- A participant will be classified as having ADAb positivity at Baseline if the Day 1, pre-dose result is ADAb+;
- A participant will be classified as overall positive if at least one post-Baseline measurement is ADAb+ (see definition above) (this includes participants who have negative and positive results at baseline);
- A participant will be classified as overall negative if at all post-Baseline visits the ADAb status is negative (this includes participants who have positive and negative results at Baseline);
- A participant will be classified as having treatment-emergent ADAb positivity when meeting one of the following criteria:
  - The Baseline result is ADAb-, and at least one post-Baseline time point is ADAb+;
  - The Baseline result is ADAb+, and at least one post-Baseline measurement shows a pre-defined fold increase in titer or units/mL (as applicable) from the Baseline value (the fold increase from Baseline required to meet these criteria will be defined with the development of the assay and will be included in the TFLs).

Analysis:

Immunogenicity will be assessed through summary tables and figures and listing of individual results by participant. All analyses will be run on the FAS, unless specified otherwise. For all tabulations, percentages will be calculated based on the number of participants with non-missing data.

- All individual participant-level ADAb results will be listed by treatment group. This will include the screening assay, confirmatory assay, and titer (if applicable).
- Number and percentage of participants with a positive and negative ADAb status will be summarized at the time of each visit and overall, separated by treatment group and for all bimekizumab treated participants.
- In addition, the first occurrence of treatment-induced ADAb positivity (based on the definitions above) will be summarized (number and percentage of participants) at each post-Baseline visit, based on the PK-PPS. This tabulation will present the number and percentage of participants at each post-Baseline visit who fulfill at least one of the above defined criteria for treatment-emergent positivity; participants will be counted in the numerator based on the earliest visit at which one of these criteria is fulfilled. At other visits, participants will be counted in the denominator (assuming a measurement is available). For all tabulations, percentages will be based on the number of observations at each visit. This summary will exclude any samples with bimekizumab concentrations confirmed to be above the drug tolerance.

A separate listing will be presented showing the bimekizumab concentrations and ADAb measurements in the same output in adjacent columns, based on the PK-PPS. The listing will include the bimekizumab concentration, ADAb status (positive or negative) and screening assay results (ACP or BCP) and confirmatory assay results if applicable (NCP or CP), together with the titer if applicable. In addition, the time since the administration of study medication will be reported (in days). ADAb samples that are negative but have drug concentration above the drug tolerance characteristics of the assay will be flagged.

Finally, individual participant plots will be presented displaying the ADAb titer and bimekizumab concentrations overlaid on the same figure for the FAS. The ADAb data will be plotted using a semi-logarithmic scale. ADAb samples that are negative but have drug concentration above the drug tolerance characteristics of the assay will be flagged on the plot.

The rules for handling values that are BLQ in the bimekizumab concentration data are described Section 4.2.1. For the ADAb data, any negative results for which there are no titers or units/mL (as applicable) available at a specific visit will be substituted with 0.001 for the purpose of the figure.

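### SAP 10.1 treats ADAb samples above drug tolerance inconsistently: one table drops confirmed positives, another counts unreliable negatives as negative

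*SAP*

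**What the plan says.** All the rules are in SAP 10.1.

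- **Sample status.** A sample counts as positive when the screening result is ACP and the confirmatory result is CP. For the opposite outcome the rule reads: "An ADAb status of negative (ADAb-) will be concluded for any participant with an ADAb level that is either BCP or ACP and NCP". ACP and BCP mean above and below the screening cut point; CP and NCP are the confirmatory results. Neither definition mentions drug concentration, and there is no third category.
- **Participant status.** One positive post-Baseline result makes a participant overall positive. For the other class: "A participant will be classified as overall negative if at all post-Baseline visits the ADAb status is negative".
- **By-visit and overall summary.** Counts of positive and negative status, on the FAS, with no drug-tolerance rule.
- **First-occurrence table.** Tabulated "at each post-Baseline visit, based on the PK-PPS". On the numerator, "participants will be counted in the numerator based on the earliest visit at which one of these criteria is fulfilled". On the denominator, "For all tabulations, percentages will be based on the number of observations at each visit". Then comes the exclusion: "This summary will exclude any samples with bimekizumab concentrations confirmed to be above the drug tolerance".
- **Listing of concentrations with ADAb results, and individual plots.** "ADAb samples that are negative but have drug concentration above the drug tolerance characteristics of the assay will be flagged"; the plots carry the same flag.

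ADAb incidence is an other/exploratory endpoint (Protocol 3, SAP 2.2.3.1). Samples are taken predose and on Days 13, 28, 56, 84, 112 and 140 (Protocol Table 1-1, footnotes). SAP 9.2.3 repeats the BE model in participants who are not ADAb positive after Baseline.

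**The concern.** Circulating drug can mask antibodies. Above the tolerance of the assay a negative result is therefore unreliable, whereas a sample that screened positive and was confirmed has shown antibody despite the drug. The SAP follows this logic in its listing and plots, which flag only negatives. The two tables do not. One discards every sample above tolerance, including the confirmed positives; the other keeps every such sample, including the unreliable negatives.

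At stake are the number of participants reported with treatment-induced ADAb, the visit at which positivity is reported to begin, and the by-visit and overall positive rates. Onset timing is the purpose of a first-occurrence table, and the early samples, which carry the most drug, are the ones most exposed to exclusion. Participants with masked antibodies would also sit in the non-positive group of the ADAb sensitivity analysis in SAP 9.2.3.

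**Working it through.** The documents give no ADAb incidence, tolerance limit or assay sensitivity, so there is no planned figure to reproduce. Every ADAb input below is an assumption.

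**1. The rules side by side, for a sample above tolerance**

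| Result | First-occurrence table | By-visit and overall summary | Listing and plots |
|---|---|---|---|
| Confirmed positive | dropped | counted positive | shown, not flagged |
| Negative | dropped | counted negative | shown, flagged |

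**2. One visit, 100 samples**

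Assume a fraction f = 0.5 above tolerance and true positivity p = 0.30 on both sides of the limit. All positives are detected below the limit and a share s = 0.5 above it, with no false positives.

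- Below: 50 samples, 15 positive, 35 negative.
- Above: 50 samples, 15 truly positive, of which 7.5 are confirmed; 50 − 7.5 = 42.5 test negative.
- Negatives at face value (by-visit rule): (15 + 7.5)/100 = **22.5%**. In general p(1 − f + fs).
- All above-tolerance samples excluded (first-occurrence rule): 15/50 = **30.0%**. In general p. The percentage is right, but 7.5 of 22.5 confirmed positives, one third, are lost from the count.
- Positives kept, only the 42.5 negatives dropped: 22.5/(100 − 42.5) = 22.5/57.5 = **39.1%**. In general p(1 − f + fs)/(1 − f + fps), which overshoots whenever s > 0.

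For p from 10% to 45%, f from 20% to 80% and s from 0 to 1, the by-visit figure runs from one fifth of the truth (f = 0.8, s = 0) to no bias (s = 1).

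**3. Timing**

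Protocol 4.2 gives a half-life of about 28 days. Assuming simple exponential decline from Day 13, concentration relative to Day 13 is 0.5^((day − 13)/28): 0.69 (Day 28), 0.34 (Day 56), 0.17 (Day 84), 0.09 (Day 112), 0.04 (Day 140).

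Suppose the limit is 25% of the Day 13 level, so samples to Day 56 are above it and later ones below.

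- Confirmed positive on Days 28 and 56 only: never counted in the first-occurrence table, yet overall positive in the FAS summary.
- Confirmed positive from Day 28 to Day 140: first counted on Day 84, which is 84 − 28 = 56 days late.

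If the limit exceeds the Day 13 level, neither participant is affected.

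**4. Simulation over the six post-dose visits**

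Assumed: 40% ever positive, half of positives above the limit detected, and an assumed pattern of onset. The limit is a multiple of the typical Day 13 concentration.

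| Limit | Overall positive | Ever counted as first occurrence | Detected positives never counted | Detected positives counted later |
|---|---|---|---|---|
| 2.0 | 40.0% | 40.0% | 0% | 0% |
| 0.50 | 37.5% | 35.1% | 6% | 18% |
| 0.10 | 34.8% | 27.5% | 21% | 47% |
| 0.05 | 33.1% | 17.6% | 47% | 36% |

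At 0.10, 85% of Day 84 samples are above the limit. The Day 84 first-occurrence percentage goes from 6.7% without exclusion to 23.8% with it. The count falls from 6.7 to about 0.238 × 15 = 3.6 per 100 participants. Percentage and count thus move in opposite directions.

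**The case against.** The best defence of the exclusion is that it is symmetrical. It removes positives and negatives alike, and in the one-visit example it returns the true 30%, whereas keeping positives and dropping only the doubtful negatives gives 39.1%. This stands against any repair that changes the numerator alone. It does not rescue the count or the onset visit, and the unbiased percentage depends on positivity being equal on both sides of the limit.

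Other points also stand. The overall FAS summary keeps every confirmed positive, and one is enough, so no detected positive is lost there. The listing and plots flag the doubtful negatives. By Days 112 and 140 drug levels are about 9% and 4% of Day 13, so late samples may limit the loss if antibodies persist and the limit lies above those levels.

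Three stronger readings are tempting, and the documents do not support them:

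- **That ADAb incidence is understated throughout.** This fails for the first-occurrence percentages, because an excluded sample is no longer an observation at that visit and leaves the denominator too.
- **That using the PK-PPS for one table and the FAS for the rest is an error.** SAP 10.1 makes the FAS the default, allows exceptions and states this one; Protocol 9.5.2 leaves the detail to the SAP.
- **That the BE conclusion is at risk.** It rests on SAP 9.2.1, which does not use ADAb status. Only one sensitivity analysis in SAP 9.2.3 does.

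**Conclusion.** The inconsistency is real and follows from the SAP text alone. In the first-occurrence table, the count of participants with treatment-induced positivity can be too low and onset can be dated too late, while per-visit percentages can stay the same or rise. In the by-visit and overall summary, this rule can only make the positive percentages too low.

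The size cannot be determined without the tolerance limit. Under the assumptions above, detected positives lost from the first-occurrence table range from none (limit at twice the typical Day 13 concentration) to 47% (limit at 5% of it). The endpoint is exploratory and described without a decision rule, and the primary BE conclusion is untouched. The point is still worth correcting, because a stated rule can give wrong counts and onset visits and the repair is cheap.

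**What to change.** In SAP 10.1:

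1. Keep every confirmed positive (ACP and CP) whatever the drug concentration, including in the first-occurrence numerator.
2. Report negatives above tolerance as a separate inconclusive category in the by-visit, overall and first-occurrence tables. Show percentages with inconclusive samples both in and out of the denominator. In the one-visit example these are 22.5% and 39.1%, on either side of the true 30%.
3. Classify a participant with no positive result and at least one inconclusive post-Baseline sample as inconclusive rather than overall negative. In SAP 9.2.3, run the ADAb sensitivity analysis with these participants included and excluded.

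The cost is SAP wording, one extra category, a second set of percentages and one repeat of a sensitivity analysis. No new data are needed, and the flag for negatives above tolerance is already planned. One consequence should be expected: if the limit is low, few participants may remain overall negative. In the simulation at 0.10, all samples to Day 56 are above the limit, so nobody sampled at those visits could be. The analysis that excludes inconclusive participants would then be small, which is a reason to show both versions.
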